
ADA=antidrug antibody, AE=adverse event, DOR=duration of response, DRR=durable response rate, IRC=Independent Review Committee, NCI-CTCAE v5.0=National Cancer Institute-Common Terminology Criteria for Adverse Events v5.0, OS =overall survival, PD-L1=programmed death-ligand 1, ORR=objective response rates, PFS=progression-free survival, PK=pharmacokinetic, RECIST 1.1=Response Evaluation Criteria in Solid Tumors Version 1.1, TEAE=Treatment-emergent adverse event.
	

Overall Design: This Phase II, multicenter, international, single-arm study is to evaluate bintrafusp alfa monotherapy in participants with advanced unresectable and/or metastatic cervical cancer with disease progression during or after platinum-based chemotherapy.

The study plans to enroll approximately 135 eligible participants from multiple study sites globally. The study is intended to enroll at least 15% of participants from China. After reaching the completion of the global study enrollment, if the number of participants enrolled in China does not meet the 15% target, enrollment may continue in China to meet local requirement until the target (at least 15%) participants from China is met.

Participants will receive an intravenous (IV) infusion of bintrafusp alfa at a dose of 1200 mg over 1 hour (-10 minutes/+ 20 minutes, i.e., over 50 to 80 minutes) once every 2 weeks.

The study includes:

- 28-day Screening period.
- Treatment with bintrafusp alfa at a dose of 1200 mg once every 2 weeks until confirmed progressive disease (PD) per Response Evaluation Criteria in Solid Tumors Version 1.1 (RECIST 1.1), death, unacceptable toxicity, or study withdrawal.
 - In the case of PD, treatment may continue if the participant's performance status (PS) has remained at least stable, in the opinion of the Investigator, the participant may benefit from continued treatment, and if other criteria are fulfilled as outlined in the protocol (refer to Section 7.1.3).
 - Participants who have experienced a confirmed complete response (CR) should continue treatment for a maximum of 24 months after confirmation of response (at the discretion of the Investigator). If the Investigator believes that a participant with confirmed CR may benefit from treatment beyond 24 months, it may be permissible to continue treatment after discussion with the Medical Monitor and the Sponsor's Medical Responsible.

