Pembrolizumab is the first checkpoint inhibitor that received approval (accelerated) from the FDA in 2018 for use as monotherapy treatment of patients with recurrent or metastatic cervical cancer with disease progression on or after chemotherapy whose tumors express PD-L1. This approval was based on the interim results from the Phase II KEYNOTE-158 study ([Chung 2019](#)):

- Among the 98 patients with previously treated advanced cervical cancer, the ORR was 12.2% (95% CI: 6.5%, 20.4%), median PFS was 2.1 months (95% CI: 2.0, 2.2 months), and median OS was 9.4 months (95% CI: 7.7, 13.1 months).

- Among the 77 patients with PD-L1 positive (CPS \geq 1), chemotherapy refractory cervical cancer, the ORR was 14.3% (95% CI: 7.4, 24.1). At the time of the publication, median DOR was not reached (range 4.1 to 18.6+ months), and median OS was 11 months (95% CI: 9.1, 14.1).
- In KEYNOTE-158, no responses were observed among the PD-L1 negative patients (CPS < 1, n=15), and 3 patients experienced best overall response as stable disease.

While the overall response rates with pembrolizumab are only comparable to other treatment options for cervical cancer patients (12.2% to 14.3%), the durability of responses are noteworthy and have presented immunotherapy as a promising treatment for this disease.

Recently, molecular characterization of cervical cancer by The Cancer Genome Atlas identified both PD-L1 and TGF- β signaling as frequently dysregulated in this disease ([The Cancer Genome Atlas Research Network 2017](#), [Roszik 2018](#)). TGF- β is historically known to be expressed in a majority of cervical cancer tissues, and its expression correlates with the extent of tumor stroma infiltrate ([Hazelbag 2002](#)). Furthermore, the role of TGF- β in cervical cancer pathogenesis is supported by data including 1) TGF- β 1 upregulation by human papilloma virus (HPV) oncoprotein E6 and E7 ([Peralta-Zaragoza 2006](#)), and 2) the correlation of poor prognosis in cervical cancer and the expression of plasminogen activator inhibitor-1, a molecule strongly and dose-dependently induced by TGF- β ([Hazelbag 2004](#)).

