4.1 Overall Design

This is a Phase II, multicenter, international, single-arm study to evaluate bintrafusp alfa monotherapy in participants with advanced unresectable and/or metastatic cervical cancer with disease progression during or after platinum-based chemotherapy. See Section 5.1 and Section 5.2 for more details for the patient population.

The primary objective is to evaluate the clinical efficacy of bintrafusp alfa based on the ORR. The key secondary objectives are safety, DOR, durable response rate (DRR), PFS, and OS. The clinical efficacy of bintrafusp alfa will also be retrospectively evaluated according to PD-L1 expression.

The study plans to enroll approximately 135 eligible participants from multiple study sites globally. The Sponsor will monitor enrollment in the study and may make determinations to limit enrollment in certain countries and/or regions in order to obtain a study population representative of global standard of care, including prior bevacizumab treatment and representative enrollment across the participating global regions (for example, asian versus non-asian countries).

The study is intended to enroll at least 15% of participants from China. After reaching completion of the global study enrollment, if the number of participants enrolled in China does not meet the 15% target, enrollment may continue in China to meet local requirement until the target (at least 15%) participants from China is met.

CCI

The study includes:

- 28-day Screening period
- Treatment with bintrafusp alfa at a dose of 1200 mg once every 2 weeks until confirmed PD per RECIST 1.1, death, unacceptable toxicity, or study withdrawal.
 - In the case of PD, treatment may continue if the participant's performance status (PS) has remained at least stable, in the opinion of the Investigator, the participant will benefit from continued treatment, and if other criteria are fulfilled as outlined in the protocol (see Section 7.1.3).
 - Participants who have experienced a confirmed complete response (CR) should continue treatment for a maximum of 24 months after confirmation of response (at the discretion of the Investigator). If the Investigator believes that a participant with confirmed CR may benefit from treatment beyond 24 months, it may be permissible to continue treatment after discussion with the Medical Monitor and the Sponsor's Medical Responsible.

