To evaluate clinical efficacy of bintrafusp alfa based on ORR	Confirmed objective response according to RECIST 1.1 assessed by an IRC	14.1.1
Secondary		
To evaluate clinical efficacy of bintrafusp alfa based on DOR	DOR according to RECIST 1.1 assessed by an IRC	14.2.8
To evaluate clinical efficacy of bintrafusp alfa based on DRR	Durable response of at least 6 months according to RECIST 1.1 assessed by an IRC	14.2.10
To evaluate clinical safety of bintrafusp alfa	Occurrence of TEAEs and treatment-related AEs including AEs of special interest	15.1, 15.2
To evaluate clinical efficacy based on PFS	PFS according to RECIST 1.1 assessed by an IRC	14.2.1
To evaluate ORR, DOR, DRR and PFS by Investigator read	Confirmed objective response, DOR, DRR, and PFS according to RECIST 1.1 assessed by Investigator	14.2.1, 14.2.6, 14.2.8, 14.2.10
To evaluate clinical efficacy based on OS	OS	14.2.13
To characterize the pharmacokinetic (PK) profile of bintrafusp alfa	The concentration observed immediately at the end of infusion (C_{EOI}) of bintrafusp alfa The concentration observed immediately before next dosing (corresponding to pre-dose or trough concentration [C_{trough}] for multiple dosing) of bintrafusp alfa	16.1
To characterize the immunogenicity of bintrafusp alfa	Immunogenicity of bintrafusp alfa as measured by ADA assay from Screening through Safety Follow-up Visit (up to 28 days after last treatment)	16.4

Objectives	Endpoints (Outcome Measures)	IAP section
To evaluate clinical efficacy of bintrafusp alfa according to PD-L1 expression	Efficacy endpoints by PD-L1 expression in tumor	16.5.1
CCI		

6 Overview of Planned Analyses

This IAP addresses the interim, primary and final analyses. If the study continues beyond 67% of the participants died, subsequent analyses may be performed but are not described in this IAP. All statistical analyses will be performed based on Clinical Data Interchange Standards Consortium (CDISC) Study Data Tabulation Model (SDTM) data using cleaned electronic Case Report Forms (eCRF) data as well as external data including tumor assessment measured by the Independent Review Committee (IRC). All data used in the analysis will be included up to a data cut-off point defined in the following subsections.

A data review meeting will be held prior to any database lock. In addition, no database can be locked until this IAP has been approved (except for emergency).

Table 2 displays an overview of the analyses to be performed for this study.

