6.1 Overview of Planned Analyses after discontinuation of NSCLC and BTC trials

The data review outcome from the 3 randomized controlled studies in NSCLC (Non-Small Cell Lung Cancer) and BTC (Biliary Tract Cancer) (MS200647-0005, MS200647-0037, MS200647_0055) appears to indicate, consistently across 2 indications, either poorer observed hazard ratios for PFS and OS in the experimental arms with bintrafusp alfa or low likelihood for bintrafusp alfa to add benefits compared to standard of care.

Based on this, the decision was made to restrict the analyses on this study MS200647-017. The analyses described in Table 2 will not be performed as planned, but one analysis based on the primary analysis cutoff of 15 February 2022 will be performed for an abbreviated CSR (aCSR).

The analyses considered relevant for this purpose are listed below:

- Participant disposition
- Important protocol deviations
- Demographics, medical history and other baseline characteristics (disease history, HPV and PD-L1 test at screening, vital signs at baseline, skin status history)
- Vaccines for COVID 19
- Previous and concomitant medications, procedures, follow-up treatments
- Treatment exposure and compliance
- Efficacy analyses:
 - ORR per RECIST 1.1 as assessed by IRC
 - ORR and DCR per RECIST 1.1 as assessed by IRC
 - Reasons for Non-evaluable BOR based on Confirmed Responses according to RECIST 1.1 as Adjudicated by IRC
 - Percent Change from Baseline in Sum of Diameters according to RECIST 1.1 as Adjudicated by IRC
 - Percent Change in Sum of Diameters between Baseline and Best Post-baseline Assessment according to RECIST 1.1 as Adjudicated by IRC and selected subgroups
 - ORR per RECIST 1.1 as assessed by IRC - Forest plot of odds ratio by subgroups
 - ORR and DCR per RECIST 1.1 as assessed by Investigator

- Concordant and Discordant Objective Response based on confirmed responses according to RECIST 1.1 between IRC and Investigator
- PFS per RECIST 1.1 as assessed by IRC
 - PFS per RECIST 1.1 as assessed by IRC - Kaplan-Meier Curve
 - PFS per RECIST 1.1 as assessed by IRC by histology and PD-L1 - Kaplan-Meier Curve
 - PFS per RECIST 1.1 as assessed by IRC - Forest plot of hazard ratio and free survival rates at 6 and 12 months by subgroups
 - PFS per irRECIST 1.1 as assessed by IRC - Kaplan-Meier Curve
- Duration of response per RECIST 1.1 as assessed by IRC
 - Duration of response per RECIST 1.1 as assessed by IRC - Kaplan-Meier Curve

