8.2 Subgroup Definition and Parameterization

Analysis of primary and key secondary efficacy endpoints may be performed on subgroups of interest as specified in this IAP Section 14. CCI

For the definition of subgroup level, data as documented in the electronic case report form (eCRF) will be taken. The category “missing” will not be included in any subgroup analysis.

In case of low number of participants within a category (< 7 participants, which is about 5% of the randomized population), categories will be pooled when meaningful.

The following subgroups will be defined and used for the subgroup efficacy analyses:

- Age
 - Age \geq 18 - < 50 years
 - Age \geq 50 - < 65 years
 - Age \geq 65 years
- Moore criteria
 - Low
 - Medium
 - High
 - Unknown
- Histology
 - Squamous cell carcinoma
 - Adenocarcinoma
 - Adenosquamous cell carcinoma
- Number of prior treatment lines (metastatic/locally advanced prior anti-cancer drug therapies (see Section 12.4))
 - 0
 - 1
 - 2
 - 3
 - \geq 4
- Pooled Region
 - North America
 - Europe
 - South America
 - Asia
 - Rest of the World (RoW)
- Prior Bevacizumab use

- Yes
 - No
- Prior anti-cancer radiotherapy (see Section 12.4)
 - Yes
 - No
- ADA status
 - Ever positive
 - Never positive
- ADA treatment-emergent status
 - Treatment-emergent ALL
- Non-treatment-emergent nAb status
 - Ever positive (for either assay TGF- β or PD-L1)
 - Never positive

All subgroups are associated with demographic and clinical variables corresponding with cervical cancer prognosis except ADA and nAb status.

For ADA and nAb status subgroups, the subgroup analyses will be performed if there are at least 3 ever positive participants.

The subgroups coming from the individual items composing the Moore criteria will be defined and used only for the Objective Response Rate (ORR) and Duration of Response (DOR) subgroup analyses:

- ECOG PS at baseline
 - ECOG PS 0
 - ECOG PS 1
- RACE from Moore criteria
 - Black or African American
 - Not Black or African American
- RACE
 - White
 - Black or African American
 - Chinese
 - Japanese
 - Korean

- Other Asian
 - Other
- Measurable disease in pelvis
 - Yes
 - No
- Disease progression-free interval from date of diagnosis < 1 year
 - Yes
 - No
- Prior platinum therapy exposure to radiotherapy
 - Yes
 - No

CCI

- PD-L1 expression at baseline measured by central lab:
 - PD-L1 expression in tumor tissue measured by 22C3 (CPS \geq 1, < 1, NE or NA)

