 - PD-L1 expression in tumor tissue measured by SP263 (vCPS (Visual element Combined Positive Score (Ventana)) \geq 5%, < 5%, NE or NA)
- HPV status collected on the “Disease History” eCRF page
 - HPV16+ or HPV18+
 - HPV+ (all other subtypes)
 - HPV-
 - Not done
- HPV status at baseline measured by central lab (see section 11.3.2)
 - High risk HPV+
 - Low Risk HPV+
 - HPV-
 - Not done

For HPV status collected on the eCRF, as they are several possibilities of testing (tumor, pre-malignant cervical lesion and other), it will be enough for a participant to have one positive value in one of the three tests to be in the associated subgroup.

CCI

To support submission purposes a subset of outputs may be repeated for the sub-populations described below:

- China: A Chinese participant is defined as a participant enrolled at a site in China
- Japan: A Japanese participant is defined as a participant enrolled at a site in Japan and of Japanese ethnicity as recorded in the case report form.

9 General Specifications for Data Analyses

This section describes any general specifications not included in subsequent sections.

Refer to Section 16.1 for PK data handling/analysis details.

The “start date” for this study is the start date of treatment.

Continuous (non-PK) variables will be summarized using descriptive statistics, i.e., the number of participants with non-missing values (n), arithmetic mean (Mean), standard deviation (StD), median (Med), 25th percentile (Q1) and 75th percentile (Q3), minimum (Min), and maximum (Max).

Qualitative variables will be summarized by frequency counts and percentages. Unless otherwise stated the calculation of proportions will be based on the number of participants of the analysis set of interest. Therefore, counts of missing observations will be included in the denominator and presented as a separate category.

Descriptive statistics by nominal visit or time point, e.g., for laboratory measurements, will include only data from scheduled visits. Unscheduled visits will be included in the derivation of baseline or worst on-treatment values.

Pharmacokinetic variables (concentrations and parameters) will also be summarized as described in Section 16.1.

The overall significance level is 2.5% one-sided. If CIs are to be calculated, these will be two-sided with a confidence probability of 95%, unless otherwise specified in this IAP.

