14.1.1 Primary Objective: Objective Response Rate

Objective Response Rate (ORR)

The ORR is the proportion of participants having a confirmed Objective Response (OR) in the analysis set.

The confirmed objective response according to RECIST 1.1 as adjudicated by the IRC is the primary endpoint of the study. The study aims to estimate the Objective Response Rate (ORR) with a sufficient level of precision and that the associated lower bound of the two-sided 95% CI is above a minimal threshold of 15%.

Confirmed Objective Response (OR)

The Confirmed Objective Response (OR) is defined as a best overall response of confirmed complete response (CR) or partial response (PR) according to RECIST v1.1 as adjudicated by IRC.

Best overall response will be assessed based on reported overall responses at different evaluation time points from the treatment start date until documented disease progression in accordance to RECIST v1.1, taking requirements for confirmation into account as detailed below. Only tumor assessments performed before the start of any subsequent anti-cancer therapies will be considered in the assessment of best overall response. If a tumor assessment was performed on the same day as start of new anti-cancer therapy, it will be assumed that the tumor assessment was performed prior to the start of the new anti-cancer therapy, therefore the tumor assessment will be included in the assessment of best overall response. Clinical deterioration will not be considered as documented disease progression. The date of the overall response assessment is the earliest date for imaging of target, non-target and new lesions of images taken at that response assessment.

Best Overall Response based on confirmed responses according to RECIST 1.1 will be derived as follows

- CR = at least two determinations of CR at least 4 weeks apart (with no PD in between)
- PR = at least two determinations of PR or better (PR followed by PR or PR followed by CR) at least 4 weeks apart (and not qualifying for a CR), with no PD in between
- SD = at least one SD assessment (or better) \geq 6 weeks after first date of study intervention and before progression (and not qualifying for CR or PR) Non-CR/Non-PD = at least one Non-CR/Non-PD assessment \geq 6 weeks after first date of study intervention and before progression with no measurable disease and does not meet criteria of CR

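### The abbreviated-CSR subgroup output for ORR is listed only as odds ratios, which in a single-arm trial show neither a treatment effect nor the ORR in any subgroup level

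*SAP*

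**What the plan says.** The design has no control group: "This is a Phase II, multicenter, international, single-arm study to evaluate bintrafusp alfa monotherapy in participants" (Protocol 4.1). The primary question is absolute. SAP 14.1.1 asks that the "associated lower bound of the two-sided 95% CI is above a minimal threshold of 15" per cent, and this is set for the overall ORR.

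SAP 6.1 withdraws the analyses of SAP Table 2 as planned and substitutes one restricted analysis for an abbreviated CSR. Its subgroup summary of ORR is "ORR per RECIST 1.1 as assessed by IRC - Forest plot of odds ratio by subgroups". In the same list, the PFS forest plot names event-free rates at 6 and 12 months beside the hazard ratio, and PFS and OS each have Kaplan-Meier curves by histology and PD-L1. Nothing further is planned unless a new safety signal appears.

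SAP Table 1 keeps as a secondary objective: "To evaluate clinical efficacy of bintrafusp alfa according to PD-L1 expression".

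On small levels, SAP 8.2 says: "In case of low number of participants within a category (< 7 participants, which is about 5% of the randomized population"), categories are pooled, but only where that makes sense. ADA and nAb subgroups run with as few as 3 ever-positive participants. SAP 8.2 describes the subgroup factors as related to prognosis, apart from ADA and nAb status.

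The visible text gives no reference level, model, interval method or zero-cell rule for the odds ratio.

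**The concern.** With everyone treated, an odds ratio between levels compares treated participants with other treated participants. It mixes any difference in prognosis with any difference in drug effect, and one arm cannot separate the two. On a forest plot it resembles the effect-modification display of a randomised trial and may be read as one.

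A reader of the abbreviated CSR will also want to know how many participants responded in a given level, and with what uncertainty. A ratio does not answer that, including for the PD-L1 levels. The waterfall plots by subgroup show individual tumour change, not an ORR with an interval. Rows with no responders would have no usable estimate under the usual Wald or logistic method, even though an absolute rate with an exact interval is always available.

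**Working it through.** **Inputs.** Planned size: "The study plans to enroll approximately 135 eligible participants from multiple study sites globally" (Protocol 1.1). Pooling cut-off: 7 participants (SAP 8.2). Interval for ORR: two-sided 95% Clopper-Pearson (SAP 14.1.1). Phase I ORR: 6/25 = 24.0% (Protocol 2.2). The documents give no subgroup sizes and no reference level, so the splits below are illustrative assumptions.

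**1. Reproducing the plan's figures.** 0.05 × 135 = 6.75 and 7/135 = 5.2%, which agrees with the stated cut-off of about 5%. The Clopper-Pearson calculation returns the protocol's own intervals: 6/25 gives 24.0% (9.4 to 45.1), 7/25 gives 28.0% (12.1 to 49.4), and 11/77 gives 14.3% (7.4 to 24.1).

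**2. The odds ratio does not determine the ORR.** With a/n₁ and c/n₂ responders, OR = a(n₂ − c) / [c(n₁ − a)].

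| Split | OR | ORRs | Exact lower bounds |
|---|---|---|---|
| 7/68 vs 7/67 | (7×60)/(7×61) = 0.98 | 10.3%, 10.4% | 4.2%, 4.3% |
| 20/68 vs 20/67 | (20×47)/(20×48) = 0.98 | 29.4%, 29.9% | 19.0%, 19.3% |

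Likewise, an odds ratio of 2 fits 5% vs 9.5% and also 24% vs 38.7%.

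**3. How often a level is empty.** P(no responders) = (1 − p)ⁿ.

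| True ORR | n = 3 | n = 7 | n = 10 | n = 15 |
|---|---|---|---|---|
| 10% | 73% | 48% | 35% | 21% |
| 20% | 51% | 21% | 11% | 3.5% |
| 24% | 44% | 14.6% | 6.4% | 1.6% |

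For n = 3 the values are 0.9³ = 0.729, 0.8³ = 0.512 and 0.76³ = 0.439. An empty level is plausible among small levels and unlikely once a level reaches about 15 at the Phase I rate.

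**4. What happens to the odds ratio then.** The Wald standard error of log OR is √(1/a + 1/b + 1/c + 1/d), where a to d are the four cell counts. It is not finite when a cell is zero. Take 0/15 vs 20/120:

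- The sample OR is 0 and there is no Wald interval.
- Logistic regression runs off to a coefficient of about −21 with a standard error of about 12,400.
- The exact conditional interval exists: 0 to 1.54.
- With the empty level as reference, the OR is infinite (exact interval 0.65 to infinity).
- Only when both levels are empty, such as 0/7 vs 0/8, is the OR undefined.

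**5. The absolute display in the same cases.** 0/7 gives 0% (0 to 41.0) and 0/15 gives 0% (0 to 21.8), the latter from 1 − 0.025^(1/15) = 0.218. Every level can be reported.

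**The case against.** **The line in SAP 6.1 is an output title, not a specification.** SAP 8.2 sends subgroup methods to Section 14. Blocks of Section 14, and of 16.5.1 on PD-L1, are redacted, so n/N, ORR columns, a reference level or a zero-cell rule may be there. This stands, and it limits the point to what the visible text names. SAP 14.1.1 as shown has no subgroup ORR estimate or odds-ratio method, and SAP 6.1 did name absolute rates for PFS, so explicit wording is still worthwhile.

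**The comparison with PFS is selective.** The OS forest plot also names only a ratio. True, but OS has Kaplan-Meier curves by histology and PD-L1, which show absolute survival. ORR has no named equivalent.

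**An odds ratio between PD-L1 levels is one legitimate summary of efficacy according to PD-L1.** It is, as a contrast. It does not give the efficacy seen in either level.

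Four stronger readings are tempting, and the documents do not support them:

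- *The odds ratio is undefined whenever a level is empty.* It is 0 or infinite with one empty level, and an exact interval exists.
- *Empty levels are likely, especially among PD-L1-negative participants.* No level sizes are given. The protocol's example, "no responses were observed among the PD-L1 negative patients (CPS < 1, n=15"), concerns pembrolizumab. For bintrafusp alfa, Protocol 2.2 reports no clear relation between PD-L1 and response, and one confirmed partial response in a PD-L1-negative patient. SAP 16.5.1 also uses a different assay and cut-off (SP263, vCPS 5%).
- *Each subgroup should be tested against 15%.* That threshold is set for the overall ORR. In small levels a lower bound above 15% would need 4/7 or 6/15, and the 0/15 interval still includes 15%.
- *The odds ratio is a purely prognostic contrast.* SAP 8.2 exempts ADA and nAb status from that description, and a single arm cannot separate prognosis from effect modification for any factor.

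**Conclusion.** The point holds as a reporting matter. As visibly specified, the only ORR summary by subgroup in the abbreviated CSR is a ratio that is not a treatment effect and that fits ORRs of about 10% and about 30% equally well (OR 0.98 in both illustrations). Where one level has no responders, it is 0 or infinite without a Wald interval. The chance of that in a single level of 7 is 14.6% at a true ORR of 24% and 21% at 20%, assuming such a level exists.

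The consequence is confined to exploratory subgroup output. The overall ORR and its exact interval are unaffected. The conclusion rests on the unredacted text; if a redacted passage already requires n/N, ORR and an interval per level, only the wording in SAP 6.1 needs aligning.

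**What to change.** Amend the SAP 6.1 line so that the forest plot shows, for each subgroup level and explicitly for the PD-L1 levels, n/N, ORR and the two-sided Clopper-Pearson 95% CI, described as descriptive estimates. If a line is drawn at 15%, state in the footnote that it is a visual reference to the overall threshold and not a subgroup test.

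If the odds ratio is kept beside these, name the reference level for each factor, label it a between-level contrast and not a treatment effect, and specify an exact or penalised method for zero cells.

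The cost is one SAP line and one figure shell. The exact interval code is already given in SAP 14.1.1, and no new data are needed.
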